4.3.1.2. Sensitivity analyses

Sensitivity analysis will be done on RS.

Sensitivity analysis: the same analysis as the primary analysis will be performed using model [1] except the fact the missing data/ intercurrent event handling will be different.

Missing data/intercurrent events handling: in order to assess the sensitivity to the missing at random (MAR) assumption, values post the following IEs:

- IE1: Study drug discontinuation for major worsening of primary Sjögren's syndrome.
- IE2: Increase or initiation of authorized medication for pSS.
- IE3: Study drug discontinuation for AE related to study drug.

will not be taken into account and will be imputed according to the missing not at random (MNAR) assumption.

The other IEs and missing data will be handled as in the primary analysis. The imputation method is detailed below and in [Appendix 7.3.2](#). A patient with all visits missing or only baseline missing will not be considered in the analysis.

Note: In case a patient is concerned by several IEs, the first event will be considered. If several IE occurred the same day, IE will be considered to be more conservative in the following order: IE1; IE2; IE3; IE4; IE5, IE6. Multiple imputation inference involves 3 consecutive phases.

1/ Imputation step:

A total of 100 imputed complete data sets will be generated.

The imputation step for missing data with a monotone pattern will be:

- For all data following study drug discontinuation for major worsening of primary Sjögren's syndrome (IE1), the values of outcome will be imputed using a reference based multiple imputation ("jump to placebo" approach) for S95011 group and using multiple imputation (MAR) for the placebo group. This approach assumes that patients from S95011 mean's response distribution is that of the placebo group patients ([Carpenter et al, 2013](#)). The imputed value will reflect the fact that these IEs are considered a bad outcome (worst case scenario).

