- For all data following increase or initiation of authorized medication for pSS (IE2) or study drug discontinuation for AE related to study drug (IE3), the values of outcome will be imputed using a reference based multiple imputation ("copy increments in placebo" approach) for S95011 group and using multiple imputation (MAR) for the placebo group. This approach assumes that patients from S95011 will exhibit an evolution of the disease similar to patients in the placebo group but starting from the benefit already obtained ([Carpenter et al, 2013](#)). The imputed value will reflect the fact that these IEs are considered a moderately bad outcome.
- For all data following another type of IE or missing data due to other reason, imputation will be done as in the primary analysis.

It is of note that for missing data with an arbitrary missing pattern, the first imputation step might be preceded by one MI approach based on MCMC method using baseline and all longitudinal data by treatment groups. If a patient has missing data before an intercurrent event, all data of this patient will be imputed using the method according to the intercurrent event.

2/ Analysis step:

The same model as [1] (described above) will be applied to each of the 100 imputed datasets.

3/ Combination step:

Statistical inferences will be generated by combining results from the 100 analyses using Rubin's formulae. The multiple imputation estimator of the difference between S95011 and placebo is the average of the individual 100 estimators. The variance of the estimator is the combination of the between- and within-imputation variability ([Carpenter and Kenward, 2007](#)).

Multiplicity handling: there is no multiplicity issue.

Statistical elements: Finally, the following elements will be provided in a summary table:

- Estimate (standard error) of the difference between adjusted treatment arm means.
- Two-sided 80% CI of the estimate.
- Two-sided 95% CI of the estimate.
- One-sided p-value.

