Regarding the estimand framework, some changes has been made between the protocol and the SAP on intercurrent events. Indeed, “*study drug discontinuation for major worsening of primary Sjögren’s syndrome or AE related to study drug*” has been split into two independent IEs as “*study drug discontinuation for major worsening of primary Sjögren’s syndrome*” (IE1) is considered more impacting than “*Study drug discontinuation for AE related to study drug*” (IE3). Thus, for sensitivity analyses, it is has been decided to handle data post the IE1 using a reference based multiple imputation (“jump to placebo” approach) while data post the IE3 are considered moderately bad outcome and will be handled using a reference based multiple imputation (“copy increment in reference” approach). In the same line, intercurrent event “*change or initiation of unauthorised medication*” from the protocol has been split into “*Increase or initiation of authorized medication for pSS*”(IE2) and “*Decrease or stop of authorized medication for pSS*” (IE6) (the unauthorized part being necessarily linked to discontinuation for major worsening this part is already handled by IE1). Here again, IE2 having more impact than IE6, post IE data will be handled using different method (respectively reference based multiple imputation “copy increment in reference” and MAR approaches) for sensitivity analyses. Finally, IE5 “*Switch of treatment group (error of dispensation)*” has been added to handle the case of the patient having a treatment switch discussed above (MAR approach).

For all efficacy analyses, it has been specified that if the regression or the imputation model does not run due to too few patients in the stratas, the four classes randomisation stratification factor will be replaced by a 2 classes composite factor: baseline intake of oral corticosteroids or antimalarial or both (yes/no). If the model is still not running, then the stratification factor will not be considered.

Finally, for the treatment policy efficacy analysis, it has been considered sufficient to consider only responders in ESSDAI defined as patients with an improvement of at least 3 points and responders in ESSPRI defined as patients with an improvement of at least 1 point.

The salivary gland tissue will not be described because of the very small number of available biopsies collected at W013.

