7.2.2. Efficacy

7.2.2.1. Intercurrent Event (IE)

IE1: Study drug discontinuation for major worsening of primary Sjögren's syndrome.

IE2: Increase or initiation of authorized medication for pSS.

IE3: Study drug discontinuation for AE related to study drug.

IE4: Study drug discontinuation for other reasons (non-medical reason, AE not related...).

IE5: Switch of treatment group (error of dispensation).

IE6: Decrease or stop of authorized medication for pSS.

For all efficacy endpoints, a flag for each intercurrent event (IE) will be created to identify the values collected post-IE vs the values before or on the IE date. As a reminder, the IE date is the date of the start of IE.

One global IE flag will be derived to determine which IE occurs first. In case a patient is concerned by several IEs, the first event will be considered. If several IE occurred the same day, IE will be considered to be more conservative in the following order: IE1; IE2; IE3; IE4; IE5, IE6.

Study drug discontinuation for major worsening of primary Sjögren's syndrome (IE1) is defined as follow:

- AE related to pSS leading to study drug discontinuation.

Increase or initiation of authorized medication (IE2) is defined as follows:

- Any increase or initiation of a new dose of corticosteroids (oral prednisone or equivalent) within 4 weeks prior to W013 visit.
- Any intramuscular, IV, or intra-articular corticosteroids within 4 weeks prior to W013 visit.
- Any increase or initiation of new dose of topical corticosteroids within 2 weeks prior to W013 visit.

CL2-95011-001 - Statistical Analysis Plan | VV-TMF-116033 | 2.0

- Any increase or initiation of new dose of antimalarials (e.g. chloroquine, hydroxychloroquine, quinacrine) after randomisation (W000).
- Any increase or initiation of new dose of methotrexate after randomisation (W000).
- Any change in route of administration of methotrexate within 4 weeks prior to W013 visit.
- Any increase or initiation of new dose of regularly scheduled Non-steroidal anti-inflammatory drugs (NSAIDs) within 2 weeks prior to W013 visit.
- Any increase or initiation of new doses of cevimeline or oral pilocarpine within 2 weeks prior to W013 visit.
- Any increase or initiation of new doses of Ocular topics (excluding artificial tears, gels, lubricants, antibiotherapy) within 90 days prior to W013 visit.

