7.3.4. Imputation step for sensitivity analysis on primary endpoint

We will implement a hybrid approach using jump to placebo approach, copy increments in placebo approach and standard multiple imputation depending if:

- **Case a:** one of the following IE occurs:
 - IE1: Study drug discontinuation for major worsening of primary Sjögren's syndrome.
- **Case b:** the following IE occurs:
 - IE2: Increase or initiation of authorized medication for pSS.
 - IE3: Study drug discontinuation for AE related to study drug.
- **Case c:** data is missing due to another type of IE (IE4, IE5, IE6) or for other reasons.

Standard multiple imputation: this method (Rubin, 1987) replaces each missing value with a set of plausible values that represent the uncertainty about the right value to impute. Each value is a Bayesian drawn from the conditional distribution of the missing observation given the observed data, made in such a way that the set of imputation properly represents the information about the missing value that is contained in the observed data for the chosen model.

Copy increments in placebo: this method (Carpenter *et al*, 2013) involves imputing the missing values in the treatment arm under MNAR by a patient's mean profile similar to the mean profile in the control arm but starting from the benefit already obtained. On the other hand, the missing values in the control arm will be imputed under MAR.

Jump to placebo: this method (Carpenter *et al*, 2013) involves imputing the missing values in the treatment arm under MNAR by a patient's mean profile similar to the mean profile in the control arm, thus losing the potential effect of the under-treatment period. On the other hand, the missing values in the control arm will be imputed under MAR

The multiply imputed data sets are then analysed by using standard procedures for complete data and combining the results from these analyses, based on the change from baseline.

Multiple imputation inference involves **3 consecutive phases** (phase 1: imputation step, phase 2: analysis step and phase 3: combination step).

Phase 1: Imputation step

To guarantee the reproduction of results, the seed will be fixed at 95011.

Step 1:

First, data collected post IE should be considered as missing (use flag derived in ADAM). In case of patient with several events (IE1="Y" and IE2="Y"...), the first one will be considered and all the values after (strictly) will be considered as missing.

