Thanks to Part1a and Part1b macros, all intermittent missing data (*i.e.* with an arbitrary missing pattern) will be first imputed using a MI approach based on MCMC method by treatment groups, in case the initial dataset has not a strict monotone missing pattern.

A total of 100 imputed partially completed datasets will be generated. This dataset will serve as a basis for the following.

Step 2:

In this sequence, remaining missing data of *DATA_BASIS* will be imputed. The nature of the IE has to be considered as the imputation rules will be different. The macro Part2a and Part2b of five macro will be used here. The methodV statement (*i.e.* a variable indicating for each record which imputation method should be used) will be used in Part2a macro. This variable would have been derived in the dataset. Then depending in IE and associated method the following will occur inside the macro:

- **Step 2a: for all missing data due to IE written in case a:**
For this specified IE (IE1), imputation will be done according to jump to placebo approach. All data (*DATA_BASIS*) will be considered to benefit of all data available at each visit. Steps for imputation are the following:
 - For patients in treatment arm: use jump to placebo approach with non-missing data from the placebo arm to impute missing data post-IE1 in the treated arm (use SAS macro "five macros").
 - For patients in control arm: impute the missing values for each imputation separately under the assumption of MAR, taking into account the baseline and value at previous and current visits in this order from *DATA_BASIS*.
 - Keep only the imputed rows in the table (patients with IEFNUM=1).
- **Step 2b: for all missing data due to IE written in case b:**
For those two specified IEs (IE2 and IE3), imputation will be done according to copy increments in placebo approach. All data (*DATA_BASIS*) will be considered to benefit of all data available at each visit. Steps for imputation are the following:
 - For patients in treatment arm: use copy increments in placebo approach with non-missing data from the placebo arm to impute missing data post-IE2/IE3 in the treated arm (use SAS macro "five macros").
 - For patients in control arm: impute the missing values for each imputation separately under the assumption of MAR, taking into account the baseline and value at previous and current visits in this order from *DATA_BASIS*.
 - Keep only the imputed rows in the table (patients with IEFNUM=2 or 3).

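### In the MNAR sensitivity analysis the first intercurrent event fixes the imputation method, so an S95011 patient with a background-medication change before stopping drug for major worsening can miss the jump-to-placebo rule

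*SAP*

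**What the plan says.** SAP 4.3.1.2 sets out three treatments of post-event ESSDAI values in the S95011 arm:

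- **IE1** (drug stopped for major worsening): jump to placebo for all data following the event. The SAP labels this a bad outcome and the worst case.
- **IE2** (increase or start of authorised pSS medication) and **IE3** (drug stopped for a related AE): copy increments in placebo, starting from the benefit already reached. The stated reason is "The imputed value will reflect the fact that these IEs are considered a moderately bad outcome".
- **IE4 to IE6** and other missing data: MAR, as in the primary analysis.

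Placebo patients are imputed under MAR throughout.

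For patients with several events the same section says "In case a patient is concerned by several IEs, the first event will be considered". It continues: "If several IE occurred the same day, IE will be considered to be more conservative in the following order", and lists IE1 through IE6.

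The appendices implement this. In 7.2.2.1, "One global IE flag will be derived to determine which IE occurs first". In 7.3.4, "the first one will be considered and all the values after (strictly) will be considered as missing", and patients are then routed by IEFNUM: 1 to jump to placebo, 2 or 3 to copy increments. IEFNUM is not defined; reading it as the number of the first event follows from these two sections. No clause moves a patient to jump to placebo if IE1 comes after another event.

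The ESSDAI responder analyses (4.3.1.3) and the ESSPRI sensitivity analysis (4.3.2) take over the same handling.

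**The concern.** Section 4.3.1.2 gives two answers for the same patient. Its IE1 bullet, read alone, puts the W013 value of anyone who stopped for major worsening under jump to placebo. The first-event note and the appendix put that value under copy increments if a medication increase came a day or more earlier, and under MAR if a medication decrease came earlier. The tie rule shows that the more conservative event is meant to govern; a one-day gap reverses that.

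What is at stake is how hard the stress test presses. This analysis is meant to show whether the result survives pessimistic assumptions about treatment failures. Some patients recorded as stopping for major worsening could receive the milder assumption, or the same one as in the primary analysis, and the result would then look somewhat more robust than it is.

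**Working it through.** **1. The plan's own figures.** Inputs from SAP 1.2: 30 and 15 patients, SD 6, one-sided 10%, estimated difference of at least 3 points.

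- SE = 6 × √(1/30 + 1/15) = 1.897.
- Significance cut-off = 1.2816 × 1.897 = 2.43, below 3, so the 3-point criterion binds.
- P(success) = 1 − Φ((3 − δ)/1.897): 70.1% at δ = 4 (stated about 70%), 50.0% at 3 (about 50%), 5.7% at 0 (around 5%) and 14.6% at 1 (stated below 14% for differences under 1).

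The design figures are reproduced closely enough to use this SE as the yardstick.

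**2. Which sequences can occur.** The last infusion is at W010 (Protocol 6.2), so IE1 can occur no later than about W010. With the windows in SAP 7.2.2.1 counted back from the scheduled W013 visit:

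| Medication change | Counts as IE2 from | IE1 can follow? |
|---|---|---|
| Antimalarials, methotrexate dose | W000 | Yes |
| Ocular topics (90 days) | about W000 | Yes |
| Oral or injected corticosteroids (4 weeks) | about W009 | Only about W009 to W010 |
| Dry-mouth/eye drugs (30 days) | about W009 | Only about W009 to W010 |
| Topical corticosteroids, NSAIDs, cevimeline/pilocarpine (2 weeks) | about W011 | No |

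IE6 uses the same windows. The SAP does not say whether an early withdrawal visit, which shares the W013 column in Protocol Table (4.1.2) 1, would move the anchor. If it does, more corticosteroid changes come into play.

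**3. Size per patient.** With δ4 and δ13 the S95011 benefit over placebo at W004 and W013, and k affected S95011 patients of 30:

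- Copy increments instead of jump: shift = k × δ4/30.
- MAR instead of jump: shift = k × δ13/30.

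The documents give no δ4. Taking δ13 = 4 (the SAP's 70% scenario) and assuming δ4 = 2:

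- k = 1: 2/30 = 0.07 and 4/30 = 0.13 points.
- k = 3: 0.2 and 0.4 points.

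Over an assumed δ4 of 0 to 3, the copy-increments shift is 0 to 0.10 for one patient and 0 to 0.30 for three. For δ13 of 3 to 4, the MAR shift is 0.10 to 0.13 per patient.

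ESSDAI is scored at W000, W004 and W013 after screening. If the first event precedes W004, only baseline is kept, and copy increments and jump coincide when baseline means are equal; that shift is then about 0. An illustrative calculation agreed: with W004 observed and an arm difference of 1.5 points there, the two methods differed by exactly 1.5; with baseline only, they were identical.

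**4. Ceiling.** The SAP assumes an overall event rate below 10%. Ten percent of 30 is 3, so k = 3 requires nearly every S95011 event of any type to be this sequence.

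**5. Against the SE.** One patient: 0.067/1.897 = 0.04 SE, or 0.133/1.897 = 0.07 SE. Three patients: 0.2/1.897 = 0.11 SE, or 0.4/1.897 = 0.21 SE. At an estimate of exactly 3.0, one-sided p is 0.057; a 0.2-point shift makes it 0.070.

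**6. Against the stress test itself.** Replacing MAR by jump to placebo costs 0.13 points per patient. Routing to copy increments removes half of that (0.07); routing to MAR removes all of it.

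**The case against.** Five points deserve weight.

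- **Dating of IE1.** SAP 7.2.2.1 defines IE1 as a pSS-related AE leading to discontinuation and dates each event at its start. If that means AE onset, a patient who worsens, then has medication increased, then stops drug has IE1 first and gets jump to placebo. A reader might infer that this sequence always escapes the rule; the documents do not support that. Nor do they settle the opposite, since the event is named as the discontinuation. The ambiguity stands.
- **Limited routes.** The windows close several paths, as the table shows. Protocol 6.3 also requires stable background therapy, and SAP 6 folds unauthorised medication into IE1. This limits frequency but does not remove the gap for antimalarials, methotrexate and ocular topics.
- **Ranking.** One might read SAP 6 as placing IE1 above every other event. It compares IE1 with IE3, and IE2 with IE6, only. The order of IE1 over IE2 rests on the tie rule and the worst-case label in 4.3.1.2, which is enough to show intent.
- **Other coverage.** The treatment-policy analysis (SAP 4.3.3) uses observed values regardless of events, and patients who stop drug have a withdrawal visit with W013 assessments (Protocol 5.6.1). This helps on general robustness, but it addresses a different estimand and leaves the MNAR analysis as written.
- **Coherence.** Taking cut-off and method from the same event is defensible under a hypothetical strategy. Sending every IE1 to jump to placebo would also count a patient dispensed the wrong treatment (IE5) who then worsens as an S95011 failure, and SAP 6 reports one potential switch. The remedy should therefore exclude IE5. Worsening after reduced background therapy (IE6) is also partly confounded, though MAR is then the most lenient choice available.

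**Conclusion.** The gap is real and small. For an S95011 patient with IE2 or IE6 first and IE1 on a later day, the first-event rule overrides the IE1 bullet and gives a milder imputation. The size is about 0.07 or 0.13 points per patient under the assumed 2-point W004 and 4-point W013 effects, with 0.2 to 0.4 points as an upper bound at the assumed event rate. The copy-increments shift favours S95011 only if W004 was observed before the first event and S95011 was ahead then. How many patients are affected depends on the window anchor and the IE1 date, neither of which the SAP fixes.

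A reader might infer that the main efficacy result is at risk. It is not: every event is handled under MAR in the primary analysis, so the order of event types does not change its imputation method, and the 3-point criterion was calibrated on that analysis. What is weakened is the worst-case label of one sensitivity analysis and of the analyses that inherit its handling.

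**What to change.** In SAP 4.3.1.2, 7.2.2.1 and 7.3.4:

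1. Keep the first event as the data cut-off.
2. For patients whose first event is IE2, IE3 or IE6, set methodV and IEFNUM from the most severe event up to W013 in the SAP's own order. A later IE1 gives jump to placebo; IE6 followed by IE2 or IE3 gives copy increments.
3. Leave patients whose first event is a treatment switch (IE5) under the existing rule.
4. State whether IE1 is dated at AE onset or at drug discontinuation, and define IEFNUM.
5. Report by arm how many patients had IE1 after another event.

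The cost is a few sentences and one derived flag. Event order and severity can be derived without treatment codes, and methodV already assigns a method record by record. The downside is that the sensitivity estimate may be slightly less favourable. If the sponsor prefers the first-event rule, it should give its reason, align the IE1 bullet with it, and show the most-severe-event version alongside.

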4.3.1.3. Supplementary analyses

Supplementary analysis will be done on RS.

Definition: the efficacy endpoint is defined as the proportion of responders in ESSDAI total score at W013.

Supplementary analysis: to assess the efficacy of S95011 (750 mg) as compared to Placebo on proportion of responders in ESSDAI after a 13-weeks treatment. Responders in ESSDAI at W013 defined as patients having improvement from baseline in ESSDAI total score of at least:

- 3 points
- 5 points
- 7 points

will be analysed separately using a logistic regression model including the fixed, categorical effect of treatment and randomization stratification factors (*rando_factor*) as well as the continuous fixed covariate of baseline value.

LOGISTIC REGRESSION MODEL: responder = baseline rando_factors treatment [2]

The assumptions underlying the model, as for instance, independence of errors, linearity in the logit for continuous variables, absence of multicollinearity, and lack of strongly influential outliers will be checked.

If the model is not running due to too few patients in the stratas, the model mentioned above will be modified. Thus, the two stratification factors in the model will be replaced by the following composite factor: baseline intake of oral corticosteroids or antimalarial or both (yes/no). If the model is still not running with the stratification factor in two classes, then the stratification factor will not be considered.

Missing data/intercurrent events handling: the handling of IEs and missing data will be the same as the primary and sensitivity analysis. Thus, imputation will be done on the change and then the imputed change values will be turned into responder/non-responder.

Multiplicity handling: there is no multiplicity issue.

Statistical elements: Finally, the following elements will be provided in a summary table:

- Estimate (standard error) of the difference between adjusted treatment arm proportions.
- Two-sided 80% CI of the estimate.
- Two-sided 95% CI of the estimate.
- One-sided p-value.

